6.4.6 Electrocardiogram

12-Lead ECGs data will be obtained during study at baseline (Core study), baseline (OLE), Visit 1, and Visit 3 through Visit 16 (End of Study/ET) and at Cardiac Follow-up (Visits 17 and 18).

A separate report will be provided by the ECG vendor.

6.4.7 Doppler Echocardiography

Doppler echocardiography will be conducted at a facility with experience for the subject's age at baseline (Core study), baseline (OLE), Visit 1, and Visit 3 through Visit 11, at End of Study/ET (Visit 16) and at Cardiac Follow-up (Visits 17 and 18).

A separate report will be provided by the ECHO vendor.

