4. SCHEDULE OF ASSESSMENTS

Table 4. Schedule of Assessments for Subjects from Core Studies ZX008-1501 and ZX008-1502, and de Novo Subjects**

Study Assessments	OLE Treatment Period				Post-Dosing Visit 17	Cardiac Follow-up Visit 18, 19	
	Visit 1 ^a	Visit 2 ^c		Visits 3-15 (Months 1, 2, 3, 6, 9, 12, 15, 18, 21, 24, 27, 30, and 33)			Visit 16 ^d (EOS/ET) Month 36
Study Day	-28 to 1 ^a	15		30, 60, 90, 180, 270, 365, 455, 545, 635, 725, 815, 905, 995	1085	1099	3 and 6 months post last dose
		Clinic	Phone				
Informed Consent	X						
Entry Criteria	X						
Demographics	X						
Medical/Neurological History	X ^a						
Epilepsy History	X ^{a,b}						
Physical Examination, complete	X ^a				X		X ^e
Physical Examination, abbreviated		X		X			X ^e
Neurological Examination, complete	X ^f				X		
Neurological Examination, abbreviated		X		X			
Vital signs	X	X		X	X		
Weight, Height, BMI	X ^a	X		X	X		
12-lead ECG	X ^a			X	X		X ^e
Doppler ECHO	X ^a			X ^{g,h}	X		X ^e
Urine Pregnancy Test ^h	X			X	X		
Clinical laboratory evaluation (hematology/clinical chemistry/urinalysis, etc)	X ⁱ	X ⁱ		X	X		
Urine THC Panel/Whole blood CBD	X ^a			X	X		
Plasma sample for background AEDs		X		X	X		
Tanner Staging (for subjects >7 to ≤ 18 years)	X ^a			X ^k	X		X ^k
C-SSRS	X ^a			X	X		
CGI-I (assessed by parent/caregiver)	X ^a			X	X		
CGI-I (assessed by principal investigator)	X ^a			X	X		
QOLCE	X ^a			X	X		
EQ-5D-5L (QoL of parent/caregiver)	X ^a			X	X		
HADS (Affect of parent/caregiver)	X ^a			X	X		
BRIEF	X ^a			X	X		

continued

Table 4. Schedule of Assessments for Subjects from Core Studies ZX008-1501 and ZX008-1502, and de Novo Subjects (continued)**

Study Assessments	OLE Treatment Period				Post-Dosing	Cardiac Follow-up	
	Visit 1 ^a	Visit 2 ^c		Visits 3-15 (Months 1, 2, 3, 6, 9, 12, 15, 18, 21, 24, 27, 30, and 33)	Visit 16 ^c (EOS/ET) Month 36	Visit 17	Visit 18, 19
Study Day	-28 to 1 ^a	15		30, 60, 90, 180, 270, 365, 455, 545, 635, 725, 815, 905, 995	1085	1099	3 and 6 months post last dose
PedsQL ⁿ	X ^a			X	X		
Study medication palatability assessment				X ^l			
Subject Diary	D	C/R/D	R	C/R/D	C/R	C/R	
Study Medication	D ^b	C/R/D	R	C/R/D	C/R/D	C/R	
Daily Diary Completion		-----X-----					
Concomitant Medication	X ^a	-----X-----					
Adverse Events	X ^a	-----X-----					
Adverse events of special interest	X ^a	-----X-----					X ^m

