AED=antiepileptic drug; BMI=body mass index; BRIEF=Behavior Rating Inventory of Executive Function; C=Collect; CBD=cannabidiol; CGI-I=Clinical Global Impression-Improvement; D=Dispense; ECG=electrocardiogram; EOS=end of study; ET=early termination; EQ-5D-5L=standardized measure of health status; HADS=Hospital Anxiety and Depression Scale; PedsQL=Pediatric Quality of Life Inventory; QoL=quality of life; QOLCE=Quality of Life in Childhood Epilepsy; R=Review

NOTE: If a subject has a birthday during the study that makes a previously unrequired assessment now required (eg, Tanner staging in a male subject who turns 8 years old during the study), this assessment(s) should be initiated at visits subsequent to the birthday.

**** de Novo subjects are subjects who did not participate in one of the core studies and may or may not be currently taking STP.**

- a: For subjects enrolling from one of the core studies use data collected at Visit 12 and Visit 13 of Study ZX008-1501 or ZX008-1502.
For de novo subjects, a screening period up to 28 days is required. During this period, informed consent is required prior to any study-related procedures. All results to determine eligibility must be reviewed prior to receiving the first dose of study medication at Visit 1.
For all subjects, clinical laboratory results and all ECHO/ECG results must be available and meet eligibility criteria prior to receiving the first dose of study medication at Visit 1.
- b: De Novo subjects must meet entry criteria 3 to 7, and 10, including having had ≥ 4 convulsive seizures (tonic, tonic-atonic, tonic-clonic, clonic) per 4-week period for past 12 weeks prior to screening, by parent/guardian report to investigator or investigator medical notes.
- c: At the discretion of the investigator, Visit 2 may be conducted as a phone visit.
- d: Or early termination.
- e: Follow-up ECG, ECHO, and physical examination will be performed 3 and 6 months after study completion or early termination.
- f: For subjects enrolling from one of the core studies, use core study Visit 12 information unless complete neurological examination is warranted based on significant changes in subject status.
- g: ECHOs will be performed at Months 1, 3, 6, 9, 12, 15, 18, 21, 24, 27, 30, and 33.

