- h: The Months 3, 6, 9, 12, 15, 18, 21, 24, 27, 30, and 33 ECHO may be performed any time within 3 weeks prior to the study visit. If a subject discontinues early from the study, the ECHO should be scheduled as soon as practical (see Table 7).
- i: Females of child-bearing potential
- j: For subjects enrolling from one of the core studies, use data collected at Visit 12 of ZX008-1501 or ZX008-1502 for Visit 1 unless clinical laboratory evaluation is warranted based on significant changes in subject status. Visit 2 clinical laboratory evaluation is optional based on subject status for all cohorts.
- k: Months 6, 15, and 27 only.
- l: Visits 3 and 4 (Months 1 and 2) only.
- m: Only adverse events related to cardiac safety will be collected at this visit (see Table 7).
- n: Not to be completed for de novo subjects >18 years old.

Table 5. Schedule of Assessments for Subjects from Core Study ZX008-1504

Study Assessments	OLE Treatment Period				Post-Dosing	Cardiac Follow-up	
	Visit 1 ^a	Visit 2 ^b		Visits 3-15 (Months 1, 2, 3, 6, 9, 12, 15, 18, 21, 24, 27, 30, and 33)			Visit 16 ^c (EOS/ET) Month 36
Study Day	1 ^a	15		30, 60, 90, 180, 270, 365, 455, 545, 635, 725, 815, 905, 995	1085	1099	3 and 6 months post last dose
		Clinic	Phone				
Informed Consent	X						
Entry Criteria	X						
Demographics	X						
Medical/Neurological History	X ^a						
Epilepsy History	X ^a						
Physical Examination, complete	X ^a				X		X ^d
Physical Examination, abbreviated		X		X			X ^d
Neurological Examination, complete	X ^c				X		
Neurological Examination, abbreviated		X		X			
Vital signs	X	X		X	X		
Weight, Height, BMI	X ^a	X		X	X		
12-lead ECG	X ^a			X	X		X ^d
Doppler ECHO	X ^a			X ^{f,g}	X		X ^d
Urine Pregnancy Test ^h	X			X	X		
Clinical laboratory evaluation (hematology/clinical chemistry/urinalysis, etc)	X ⁱ	X ⁱ		X	X		
Urine THC Panel/Whole blood CBD	X ^a			X	X		
Plasma sample for background AEDs		X		X	X		
Tanner Staging (for subjects > 7 years old)	X ^a			X ^j	X		X ^j
C-SSRS	X ^a			X	X		
CGI-I (assessed by parent/caregiver)	X ^a			X	X		
CGI-I (assessed by principal investigator)	X ^a			X	X		
QOLCE	X ^a			X	X		
EQ-5D-5L (QoL of parent/caregiver)	X ^a			X	X		
BRIEF	X ^a			X	X		
Healthcare utilization questions	X ^a			X	X		

continued

Table 5. Schedule of Assessments for Subjects from Core Study ZX008-1504 (continued)

Study Assessments	OLE Treatment Period				Post-Dosing	Cardiac Follow-up	

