OLE	10	10	Month 18 (OLE)	500 to 589	545
OLE	11	11	Month 21 (OLE)	590 to 679	635
OLE	12	12	Month 24 (OLE)	680 to 774	730
OLE	13	13	Month 27 (OLE)	775 to 864	820
OLE	14	14	Month 30 (OLE)	865 to 954	910
OLE	15	15	Month 33 (OLE)	955 to 1044	1000
OLE	16	16	Month 36 (OLE)	1045 to 1109	1095
OLE	17/OLE Last Visit**	99	Last Value	Day 2 to Visit 17 date	

*For multiple measurements within a time window, please use the closest to the target time point. Note that measurements occurring on the end date of a phase/period or start date of a new phase/period are assigned to the preceding phase/period. For example, measurements taken on OLE Study Day1 are assigned as Baseline (OLE). Visits where the Tanner Stage is not scheduled for collection are included due to early termination visits occurring between scheduled visits.

**The last observation in the time window will be used. [This is an exception from the rule in the preceding note.]

Table 7e. Time Intervals for ECGs and ECHO*

Analysis Phase/Period	Scheduled Visit Number in ZX008-1503	Analysis Visit*	Time Interval (label on output)	Time Interval (Day)	Target Time Point (Day)
Pre-OLE	1	1	Baseline (OLE)	<1	1
OLE	3	3	Month 1 (OLE)	2 to 44	30
OLE	4	4	Month 2 (OLE)	45 to 74	60
OLE	5	5	Month 3 (OLE)	75 to 134	90
OLE	6	6	Month 6 (OLE)	135 to 224	180
OLE	7	7	Month 9 (OLE)	225 to 314	270
OLE	8	8	Month 12 (OLE)	315 to 409	365
OLE	9	9	Month 15 (OLE)	410 to 499	455
OLE	10	10	Month 18 (OLE)	500 to 589	545
OLE	11	11	Month 21 (OLE)	590 to 679	635
OLE	12	12	Month 24 (OLE)	680 to 774	730
OLE	13	13	Month 27 (OLE)	775 to 864	820
OLE	14	14	Month 30 (OLE)	865 to 954	910
OLE	15	15	Month 33 (OLE)	955 to 1044	1000
OLE	16	16	Month 36 (OLE)	1045 to 1109	1095
OLE	17/Final Visit**	99	Last Value	2 to Visit 17 date	
Post-OLE	18	999	Cardiac FU 1	Visit 17 date + 1, to Visit 18 date	
Post-OLE	19	9999	Cardiac FU 2	Visit 18 date +1, to Visit 19 date	

*For multiple measurements within a time window, please use the closest to the target time point. Note that measurements occurring on the end date of a phase/period or start date of a new phase/period are assigned to the preceding phase/period. For example, measurements taken on OLE Study Day1 are assigned as Baseline (OLE).

** The last observation in the time window will be used. [This is an exception from the rule in the preceding note.]

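### SAP 6.4.7 gives an ECHO visit list that contradicts Tables 4, 5 and 7e, and the shared ECG/ECHO windows in Table 7e label some compliant Month 3 ECHOs as Month 2

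*SAP*

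**What the plan says.** **Section 6.4.7 (Doppler Echocardiography).** Besides the baselines, ECHO is placed at "Visit 1, and Visit 3 through Visit 11, at End of Study/ET (Visit 16"), with cardiac follow-up at Visits 17 and 18. The section then leaves reporting to a separate vendor report.

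**Tables 4 and 5 (Section 4).** The column for these visits reads "Visits 3-15 (Months 1, 2, 3, 6, 9, 12, 15, 18, 21, 24, 27, 30, and 33"), with study days "30, 60, 90, 180, 270, 365, 455, 545, 635, 725, 815, 905, 995". Visit 16 is Month 36, Day 1085. Visit 17 is the post-dosing visit, and Visits 18 and 19 are the cardiac follow-up. Footnote g of Table 4 and footnote f of Table 5 both state: "ECHOs will be performed at Months 1, 3, 6, 9, 12, 15, 18, 21, 24, 27, 30, and 33". Footnote h of Table 4 and footnote g of Table 5 add that from Month 3 on the "ECHO may be performed any time within 3 weeks prior to the study visit".

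**Table 7e (Section 6.1.6).** A single set of windows, titled "Time Intervals for ECGs and ECHO", serves both assessments. Month 1 is Days 2-44, Month 2 is Days 45-74 (target Day 60) and Month 3 is Days 75-134 (target Day 90). There are rows for Months 24, 27, 30 and 33, and for cardiac follow-up at Visits 18 and 19.

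**Section 6.4.6 (Electrocardiogram), for comparison.** ECG runs without a break: "Visit 1, and Visit 3 through Visit 16 (End of Study/ET"). It too numbers the cardiac follow-up as Visits 17 and 18.

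**The concern.** The primary objective is long-term safety, and Section 6.9 describes ECHO as the examination through which potential valvulopathy and pulmonary hypertension are detected. Whoever prepares the ECHO report needs one visit list and one rule for assigning an ECHO to a time point. This SAP gives two visit lists. The one in the ECHO section itself stops at Month 21 and resumes only at the end of study, across the period when cumulative exposure is longest.

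The window rule has a different fault. It was built around ECG visits, which include Month 2, and takes no account of the 3-week allowance for ECHO. A site that follows the footnote exactly can produce a Month 3 ECHO that the analysis labels Month 2, a time point at which the footnotes schedule none. That subject would then have no Month 3 value, unless there is a second ECHO on Days 75-134.

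**Working it through.** **Step 1: map visits to months and days (Tables 4 and 5).** Visit 3 = Month 1 (Day 30), Visit 4 = Month 2 (Day 60), Visit 5 = Month 3 (Day 90), Visit 6 = Month 6, and so on to Visit 11 = Month 21 (Day 635), Visit 15 = Month 33 (Day 995) and Visit 16 = Month 36 (Day 1085).

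**Step 2: compare the ECHO lists before Visit 16.**

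| Source | Months with ECHO | Cardiac follow-up |
|---|---|---|
| 6.4.7 | 1, 2, 3, 6, 9, 12, 15, 18, 21 | Visits 17, 18 |
| Footnotes to Tables 4 and 5 | 1, 3, 6, 9, 12, 15, 18, 21, 24, 27, 30, 33 | Visits 18, 19 |
| Table 7e rows (ECG and ECHO together) | 1, 2, 3, 6, then every 3 months to 33 | Visits 18, 19 |

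In the footnotes but not in 6.4.7: Months 24, 27, 30 and 33, which is 4 of 12. In 6.4.7 but not in the footnotes: Month 2. Read literally, 6.4.7 leaves 1085 - 635 = 450 days between on-treatment ECHOs. That is 450 / 30.4 = 14.8 months with the SAP's own conversion factor (6.1.8).

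**Step 3: place the permitted Month 3 ECHO days in Table 7e.** For a visit on Day V, the permitted days run from V - 21 to V, which is 22 days. With V = 90 they are Days 69 to 90. The Month 2 window ends on Day 74, so Days 69, 70, 71, 72, 73 and 74 fall in it: 6 of 22. These are ECHOs done 16 to 21 days before the visit.

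**Step 4: vary the Month 3 visit day.** Month 3 opens on Day 75, so the number of permitted days falling too early is 75 - (V - 21) = 96 - V, or zero if that is negative.

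- V = 84: 96 - 84 = 12 of 22
- V = 90: 96 - 90 = 6 of 22
- V = 96 or later: 0 of 22

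**Step 5: check the later visits.** At each scheduled day from Month 6 to Month 33, the earliest permitted ECHO is still inside its own window. For example, Month 6 gives 180 - 21 = Day 159 against a window of Days 135-224, and Month 33 gives 995 - 21 = Day 974 against Days 955-1044. The result is 0 of 22 days misassigned at every one of these visits.

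**Step 6: derive windows without Month 2.** In this part of Table 7e each boundary is the midpoint between adjacent targets, with the midpoint day going to the later visit: (30 + 60)/2 = 45, (60 + 90)/2 = 75, (90 + 180)/2 = 135. Without Month 2, the boundary between Months 1 and 3 is (30 + 90)/2 = 60. That gives Month 1 = Days 2-59 and Month 3 = Days 60-134. The number of permitted Month 3 days falling too early becomes 60 - (V - 21) = 81 - V, which is zero for any visit from Day 81 on. A start at Day 69 gives 69 - (V - 21) = 90 - V. That is zero for a Day 90 visit but 6 for a Day 84 visit.

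**The case against.** The strongest reply is that no analysis in this SAP runs on 6.4.7. ECHO results go to a separate vendor report, and the planned output list in Appendix 1 has no ECHO safety table, figure or listing. Section 6.9 sends every ECHO performed in the trial to the central reader. Tables 4, 5 and 7e all keep Months 24 to 33. The list in 6.4.7 looks like text left from the 24-month design: Section 3.1 still describes a 24-month treatment period, and 6.3.3.3 still calls EOS/ET Visit 12.

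Much of this stands, and it rules out three stronger readings.

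- A reader might infer that a third of the scheduled ECHOs are dropped and that the third year has no ECHO data. The SAP does not show this. It would follow only if one descriptive sentence overrode both schedules and the window table.
- A reader might call the Month 2 row in Table 7e spurious. It is not, because ECG is scheduled at Visit 4 and shares the table.
- A reader might take 6 of 22 as the share of subjects affected. It counts calendar days. The SAP gives no distribution of ECHO timing, so no number of subjects can be derived.

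It can also be said that Section 6.1.6 deliberately separates analysis windows from scheduling windows. That explains why data are placed by actual day. It does not explain why an ECHO window should cut across the footnote's allowance and move compliant data to a time point with no scheduled ECHO.

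The reply does not remove the contradiction. Table 7e still sets ECHO windows, and the section headed Doppler Echocardiography still gives a different visit list.

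**Conclusion.** Two inconsistencies stand, both modest and both cheap to correct.

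1. Section 6.4.7 disagrees with Tables 4 and 5 on 4 of 12 scheduled ECHOs before Visit 16 and on Month 2. It disagrees with Tables 4, 5 and 7e on the numbering of cardiac follow-up. Loss of the Month 24 to 33 data is a risk that depends on 6.4.7 being followed literally. It is not an established consequence. Which ECHO schedule is right is not judged here.
2. Table 7e labels as Month 2 a compliant Month 3 ECHO done 16 to 21 days before a Day 90 visit. This covers 6 of 22 permitted days, more if the visit is early and none from Day 96 on. Months 6 to 33 at their scheduled days are unaffected.

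The second result assumes that the Table 4 and 5 footnotes on months and on the 3-week allowance stand, and that Table 7e governs whatever ECHO summaries are produced.

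**What to change.** Reconcile 6.4.7 with Tables 4, 5 and 7e, both for the on-treatment visits and for the numbering of the cardiac follow-up visits, so that the ECHO report works from one list. Correct the same follow-up numbering in 6.4.6.

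In Table 7e keep the Month 2 row for ECG. If the footnotes stand, add separate ECHO windows without Month 2. The table's midpoint rule gives Month 1 = Days 2-59 and Month 3 = Days 60-134. Any Month 3 start no later than Day 69 removes the problem for a Day 90 visit, provided the Month 1 window is extended to meet it. The midpoint choice also covers visits as early as Day 81. Opening Month 3 at Day 45 is not advisable, because Days 45-59 are nearer the Month 1 target.

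The cost is a few words in two sections and one added window table, with no change to data collection.

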6.4.8 Tanner Staging

Tanner Staging will be assessed for subjects >7 years old during the study at baseline (Core) period, baseline (OLE), and at Visit 3 through Visit 15 and EOS/ET (Visit 16). Conceptually, pubertal maturation can be described in terms of sequence, timing, and tempo. Puberty consists of a series of predictable events, and the sequence of changes in secondary sexual characteristics has been categorized by several groups. The onset and progress of pubertal changes will be recorded on a 5-point scale for boys and girls separately. Boys are rated for genital development and pubic hair growth through stage I to stage V. Girls are rated for breast development and pubic hair growth through stage I to stage V.

The number and percentage of subjects in each Tanner Stage will be presented for baseline (Core) and EOS by treatment group separately for boys and girls.

All Tanner staging data will be presented in the subject data listing.

6.4.9 Laboratory Parameters

Blood samples for clinical laboratory evaluation will be obtained at each study visit as indicated in the schedule of assessments given in Table 1. Laboratory safety parameters will be analyzed by a central laboratory using standard validated methods.

The following continuous laboratory parameters will be analyzed:

- Hematology: hemoglobin, hematocrit, erythrocytes, erythrocyte mean corpuscular volume, leukocytes, neutrophils, lymphocytes, monocytes, eosinophils, basophils and platelets
- Blood Biochemistry: albumin (ALB), alkaline phosphatase (AP), alanine aminotransferase (ALT; SGPT), aspartate aminotransferase (AST; SGOT), blood urea nitrogen (BUN), calcium (Ca), carbon dioxide (CO₂), chloride (Cl), creatinine, creatine kinase, gamma-glutamyl transferase (GGT), globulin, glucose, lactate dehydrogenase (LDH), phosphorus, potassium (K), sodium (Na), thyroid function, thyroid stimulating hormone (TSH), total bilirubin, direct bilirubin, total cholesterol, total protein, triglycerides, uric acid.
- Tests of growth and precocious puberty: Growth hormone (GH), insulin-like growth factor-1 (IGF-1, low sensitivity), prolactin, Luteinizing Hormone (LH), Follicle Stimulating Hormone (FSH), testosterone, estradiol
- Epilepsy genotype panel
- Coagulation: Prothrombin time (PT)/International normalized ratio (INR), activated partial thromboplastin time (PTT)
- Whole blood cannabidiol
- Urinalysis: analysis for pH, glucose, ketones, nitrite, protein, bilirubin, urobilinogen, leukocyte esterase, and occult blood. Microscopic analysis will be performed for blood, all cell types, and casts.

- Urine pregnancy test: Urine pregnancy testing will be performed in female subjects of childbearing potential.
- Urine THC panel

Observed continuous laboratory data will be descriptively summarized by type of laboratory test/parameter overall and by treatment group. Changes from baseline will also be presented for all continuous laboratory parameters overall and by treatment group over time.

Categorical laboratory parameters will be summarized by presenting the number and percentage of subjects by visit for all subjects and by treatment group.

All laboratory values (including invalid values, reference ranges, and possible flags (low, high,)) will be presented in the subject data listings.

A listing of subjects with extreme laboratory results will be provided.

6.4.10 Columbia-Suicide Severity Rating Scale

The Columbia–Suicide Severity Rating Scale (C-SSRS) is an assessment tool that evaluates suicidal ideation (including intent), and behavior. Baseline (core study) data were collected in the screening visit (Visit 1) of the Core study using the C-SSRS Children’s Baseline/Screening Assessment. For the current study, baseline (OLE) Treatment period data and Visits 3 through Visit 15 and EOS/ET (Visit 16) data are collected using the C-SSRS Children’s ‘Since Last Visit Assessment.

Subjects who are younger than 7 years chronologically, or who are judged by the investigator not to have the mental capacity to understand the questions as specified on the C-SSRS, will not complete the rating. The investigator should use his/her judgment to substitute intellectually appropriate questions to probe the tendency for self-harm.

If a subject with the intellectual capacity to complete the C-SSRS reaches 7 years of age during the study, use of the C-SSRS should be initiated at subsequent visits.

6.4.10.1 Suicidal Ideation

[figure not shown]
The following outcomes are C-SSRS categories and have binary responses (yes/no):

Suicidal ideation is assessed as a “yes” answer at any time during the OLE treatment period to any one of the five questions (1-5) above. The number and percentage of subjects with suicidal ideation will be presented, as well as the number and percentage having a “yes” response to each category (1-5) at least once during the OLE period. The denominator will be the number of subjects completing the C-SSRS at least once during the OLE treatment period.

6.4.10.2 Suicidal Behavior

The following outcomes are C-SSRS categories and have binary responses (yes/no):

Suicidal behavior is assessed as a “yes” answer at any time during the OLE treatment period to any one of the five questions (6-10) above. The number and percentage of subjects who had suicidal behavior, as well as the number and percentage having a “yes” response to each category (6-10) at least once during the OLE period. The denominator will be the number of subjects completing the C-SSRS at least once during the OLE treatment period.

6.4.10.3 Suicidal Ideation or Behavior

An overall composite will be provided similar to the suicidal ideation and behavior composite endpoints but will instead count a subject if any of the C-SSRS questions 1 through 10 is marked as “yes” any time during the OLE period.

